## Study Summary

|  |   |
|--|---|
| Title                                 | REMOTE OBSERVED DOSING TO IMPROVE SUBOXONE COMPLIANCE IN CLINICAL PRACTICE  |
| Short Title                           | RODISC  |
| IRB Number                            |   |
| Protocol Number                       | 830028 (JIT)  |
| Methodology                           | Two-Group RCT examining remote observed dosing. All participants receive Suboxone.  |
| Study Duration                        | 13 weeks  |
| Study Center(s)                       | University of Pennsylvania   |
| Objectives                            | To test the preliminary efficacy of using remote adherence monitoring in buprenorphine (Suboxone®) treatment for OUD  |
| Number of Subjects                    | 40 subjects   |
| Main Inclusion and Exclusion Criteria | Opioid use disorder. Men and women over 18 years of age. Subjects must have current DSM 5 diagnosis of opioid use disorder. Subjects must be in good health and psychiatrically stable. They must have no other substance use disorder except tobacco use disorder or cannabis use disorder. Comorbid alcohol use disorder will be accepted if alcohol use disorder is not severe enough to require a medical alcohol detoxification. Subjects must not have received buprenorphine maintenance treatment within the past 3 months and must not have a current diagnosis of chronic pain requiring opioids. |
| Intervention                          | 2 Group RCT:
Group 1 (control): Attention match group that mirrors current clinical care
Group 2 (treatment): Remote observed dosing of Suboxone  |

CONFIDENTIAL

|  |  |
|--|--|
| Statistical Methodology         | Buprenorphine adherence will be measured using two-times-weekly creatinine normalized quantitative urine levels for buprenorphine and norbuprenorphine. Rates of illicit opiate use will be compared between the groups using combinations of urine drug screens(UDS) and TLFB self-reports obtained at each visit. At each office visit, subjects will complete standard questionnaires on mood, health behaviors, risky behaviors, and craving, and report all drug and alcohol use that has occurred since their last office visit. Submission of videos will be recorded (date and time) and assessed daily for compliance (i.e., taking the medication as prescribed).  |
| Data and Safety Monitoring Plan | 
Data will be collected by trained study staff with standardized forms using only a study number and initials to identify the participant. A code that links the participant to the study will be kept confidential by the study team in a password protected secure database. The clinical research coordinator and fellow staff members will be responsible for collecting and checking all clinical data. This includes ensuring that all fields are completed appropriately, that the clinical database is complete and accurate and all corrections are done according to GCPs. Any inconsistencies/ deviations will be documented and reviewed by the PI.
 
All data collection is HIPAA compliant. The CSA supports the appropriate privacy of all clinical and research data collected as part of any study. We follow Penn's policy in the use and disclosure of protected health information in research in a manner that respects the patient's privacy in accordance with the "Privacy Rule" promulgated under the Health Insurance Portability and Accountability Act (HIPAA) and other applicable laws. All staff receive appropriate HIPAA training. All participants sign a combined Informed Consent and HIPAA-authorization form, receive a copy of this form, and receive a notice of Penn's privacy practice. HIPAA signed forms are retained in locked file cabinets with participants' source documents. Data analysis will be conducted by the Center statistician, [name], with assistance from the PI.
 |

## Background and Study Rationale

This study will be conducted in full accordance with all applicable University of Pennsylvania Research Policies and Procedures and all applicable Federal and state laws and regulations including the following regulations as they apply 45 CFR 46, 21 CFR Parts 50, 54, 56 All episodes of noncompliance will be documented.

### 1 Introduction

Opioid Use Disorder is a major public health problem, with high relapse rates and a strong association with negative health consequences. Suboxone (buprenorphine + naloxone) is an efficacious medication that is typically administered in an office-based setting; however, compliance rates are near 50% and diversion is a significant problem. This project proposes to develop and test the use of remote compliance monitoring of Suboxone to improve medication adherence and treatment outcomes.

CONFIDENTIAL

### **1.1        *Background and Relevant Literature***

Opioid use disorder (OUD) is a significant public health problem. About 2 million Americans meet criteria for opioid use disorder involving prescription pain relievers and an additional 591,000 Americans meet criteria for a heroin use disorder (Center for Behavioral Health Statistics and Quality 2016). The rise in prescription opioid use in the US has resulted in a dramatic increase in heroin use, as prescription opioid users switch to heroin when their access to prescription opioids becomes limited (Peavy et al. 2012; Cicero, Ellis, and Surratt 2012; Cicero et al. 2014, 50). Opioids (including prescription opioids and heroin) killed more than 33,000 people in 2015, more than any year on record (CDC 2016). Nearly half of all opioid overdose deaths involve a prescription opioid.(Rudd et al. 2016) In addition to opioid overdose deaths, opioid use is associated with a number of medical problems, especially when used intravenously. Needle sharing and sexual practices place heroin users at high risk for human immunodeficiency virus infection and hepatitis c as well as other infectious diseases (Chen et al. 2015; Richard S. Garfein et al. 1996). Heroin use is associated with high utilization of emergency services (McGeary and French 2000).

Effective treatments for OUD are available but underutilized. From 2004-2013 only 21% of patients with an OUD received any treatment (Saloner and Karthikeyan 2015). This is despite the fact that there are currently 3 efficacious medications available to treat this disorder: methadone, naltrexone (Vivitrol®), and buprenorphine (Suboxone®). Methadone maintenance treatment (MMT) has been available the longest of the three and has been shown to a very efficacious treatment (Ball and Ross 1991) As an opiate agonist, methadone is able to alleviate opiate withdrawal symptoms, reduce opiate craving and, at higher doses, reduce the ability of illicit opiates to cause intoxication (Ward et al. 2009). However, there are a several aspects of MMT that are less attractive. For example, MMT occurs exclusively in the context of an Opiate Treatment Program (OTP), where dosing occurs daily at set times. Such programs require a large time investment from participants, as they must attend the clinic daily within set dosing hours. Another common problem with MMT relates to the associated side effects that can diminish patient compliance including weight gain and cognitive impairment (Curran et al. 2001; Mendelson et al. 1996; Nolan and Scagnelli 2007; Pirastu et al. 2006; Prosser et al. 2006). Lastly, federal regulations limit access to MMT making it logically impractical for many patients (Johnson et al. 2000; Substance Abuse and Mental Health Administration 2015).

Buprenorphine, a partial agonist that exerts significant actions at the mu opioid receptor, has also been shown to be effective for the treatment of OUD (Johnson et al. 1995; Liebson et al. 1988; Johnson, Jaffe, and Fudala 1992). It offers agonist substitution that alleviates opiate withdrawal and reduces opiate cravings—thereby reducing opiate use (Gowing, Ali, and White 2009; Greenwald et al. 2007; W Ling and Wesson 2003). Buprenorphine has a higher affinity for the mu opiate receptor than all available full opiate agonists offering antagonist blockade that prevents patients from experiencing a high from illicit opiates (Greenwald et al. 2007; W. K. Bickel et al. 1988; Warren K. Bickel and Amass 1995). Because it is a partial agonist and not prone to overdose, it is considered to be safe enough to dispense out of a clinician's office as opposed to an OTP (Center for Substance Abuse Treatment 2004). The availability of buprenorphine treatment outside of an OTP has significantly expanded the availability of effective treatment for OUD and is associated with reducing disparities related to treatment access (Bonhomme et al. 2012; Kumari et al. 2016; Stanton 2006).

While initial studies reported little evidence of buprenorphine diversion (Stanton 2006), more recent studies have indicated buprenorphine is prone to diversion and poor adherence that can significantly diminish its safety and efficacy (Kumari et al. 2016; Tkacz et al. 2012). In these US clinical trials, adequate adherence to buprenorphine has been shown to occur in fewer than

CONFIDENTIAL

50% of subjects who are prescribed the medication. In a trial involving 50 African American subjects with opioid use disorder participating in office based buprenorphine treatment, it was found that only 48% of the subjects were adherent to the medication as defined as having 80% or more of their visits associated with a positive UDS for buprenorphine (Kumari et al. 2016). In another trial involving 703 subjects with opioid use disorder only 41% of the subjects took buprenorphine 80% of the days it was prescribed (Tkacz et al. 2012). Finally in an examination of medical and pharmacy claims data over a year, only 32% of patients participating in office based buprenorphine treatment took buprenorphine on 80% or more days (Tkacz et al. 2014).

Poor adherence to buprenorphine treatment has been associated with a number of negative outcomes including poor treatment retention of patients participating in office based treatment (Matson et al. 2014). Compared to patients with good adherence, poorly adherent patients in office based buprenorphine treatment were ten times more likely to relapse to opioid use (Tkacz et al. 2012).

The growth in cell phone use creates an unprecedented opportunity to improve medication adherence (Krishna, Boren, and Balas 2009; Lester et al. 2010; Horvath et al. 2012; Granholm et al. 2011; Pop-Eleches et al. 2011). The use of Remote Observed Dosing (ROD) allows us to reach underserved, at-risk populations (Hoffman et al. 2010). In a study with cannabis dependent patients using ROD that was directly observed (DOT) over Skype for three weeks, every morning 20 participants were video called by staff who observed consumption of the study medication. Adherence was confirmed 96% of the time and was also assessed with weekly face-to-face visits, pill counts, and plasma drug levels (DeWorsop et al. 2016).

The ROD protocol we are proposing in this study is very similar to protocols used in studies with pediatric patients receiving iron chelation therapy and adult patients receiving anti-tuberculosis treatment that allows the user to video record dosing (Leonard et al. 2017; R. S. Garfein et al. 2015). Leonard and colleagues conducted a pilot study to examine the feasibility of using a smartphone app to improve compliance to iron chelation. Self-report adherence rates to chelation therapy are around 71%-76% and are as low as 43% based on pharmacy refill rates (Leonard et al. 2017). The protocol these researchers used involved: 1) patient recording daily videos of at-home medication administration and 2) provider feedback through cell phone messaging. The mobile ROD protocol was feasibly implemented in a clinic setting and reported high levels of compliance, disease knowledge retention, and acceptance among patients. In another pilot study with adult patients in Mexico and the US who were receiving anti-tuberculosis treatment, ROD was used to monitor compliance (R. S. Garfein et al. 2015). This protocol involved patients using a smartphone to record videos of themselves taking the medication and uploading the video to a secure website to document compliance. The research staff sent text message reminders—one before the doses were due and one after missed doses. Garfein and colleagues reported that adherence was similar in Mexico (96%) as in the US (93%) and ROD was preferred over observed in office dosing. In addition, ROD patients felt the technique was more confidential; never or rarely experienced problems recording the videos and 100% would recommend ROD to others (R. S. Garfein et al. 2015).

To address this need we recently completed a feasibility study of remote observed Suboxone® dosing to determine whether we could enroll and retain participants in such a study (**UPENN Protocol # 816651**). The observed dosing protocol we used was similar to the ones used to examine the feasibility of directly observed therapy (DOT) (DeMaio et al. 2001; DeWorsop et al. 2016). In our feasibility study, 10 participants were enrolled. Each participant received 12 weeks of Suboxone® during the study. Participants attended weekly in-office sessions where they took an observed dose of Suboxone® and then took the remaining weekday doses (M-F) while on a

CONFIDENTIAL

video Skype call with study staff. Data from that study reveal low rates of continued opioid use while on Suboxone® and high rates of Skype-observed doses. All urines tested during the study were buprenorphine positive, demonstrating excellent adherence with the treatment. In addition, self-reports of opiate use corresponded to urine drug screen results, and only one participant continued to test positive for opioids intermittently during the study. ***Participants successfully completed 100% of required in-office visits, and 90% of scheduled Skype calls. Perhaps more important, participants did not find the daily Skype calls to be burdensome.***

However, the pilot study did not have a control group and because the clinic was only open Monday-Friday, we did not observe dosing on the weekends. While this is true for many physician offices and community based treatment providers, it is problematic because weekends are often a high risk time for drug users. It is important to observe dosing 7 days a week in order to ensure optimum adherence and avoid diversion. It is equally important to determine if ROD improves buprenorphine adherence compared to an attention-matched control group.

[name] has developed a protocol that uses a ***smartphone to video record buprenorphine dosing and automatically sends this recording through HIPAA compliant means to clinical staff who can then review it at a convenient time and location.*** Her protocol also uses SMS text messaging to communicate with patients. To address the feasibility of patients with an OUD using this technology, [name] conducted a pilot study with 71 patients in OUD treatment locally regarding the feasibility and usability of such a technology. The preliminary data indicated:

- While 95% of patients had a cell phone, the majority of them (76%) had “pay as you go” plans with limited data capabilities. In addition, 71% reported changing their cell phone regularly.
- 87% reported sending and receiving SMS text messages daily, 60% used the video option on their phones to send videos, 54% watched videos online, and 53% used an “instant message app”.
- 78% reported they would take part in a text messaging program to help prevent relapse and 75% reported they would be receptive to a cell-phone based OUD intervention.

***These findings suggest using the proposed platform to monitor buprenorphine dosing is both feasible and would be welcomed by patients undergoing opioid treatment.***

## 2 Study Objectives

ROD has the potential to 1) improve adherence, 2) reduce the risk of diversion, and 3) increase access to buprenorphine treatment.

### 2.1 Primary Objective

- The overarching aim of this behavioral intervention is to test the preliminary efficacy of using remote adherence monitoring in buprenorphine (Suboxone®) treatment for OUD. For the ROD group, we will calculate the within-patient proportion of study days on which video captured adherence, as per protocol. We will use these data to compare observed adherence rates in this group to rates reported in prior studies and to the attention control group.

CONFIDENTIAL

## **2.2 Secondary Objectives (if applicable)**

- Rates of illicit opiate use will be compared between the groups using combinations of urine drug screens (UDS) and TLFB self-reports obtained at each visit.

## **3 Investigational Plan**

Forty patients with OUD, who are not currently prescribed buprenorphine, will be recruited through the University of Pennsylvania's Center for the Studies of Addiction (CSA), an outpatient substance abuse treatment facility. Potential participants will be screened for physical and psychological appropriateness for inclusion in the study using the CSA standard intake procedures. This includes a psychosocial diagnostic evaluation, a medical exam, urine and blood tests, and an EKG (see Measures for full description of screening assessments). Participants who are appropriate for the trial will be inducted onto Suboxone® using standard office based induction as described in the ASAM National Practice Guideline for the Use of Medications in the Treatment of Addiction Involving Opioid Use (Kampman and Jarvis 2015).

All patients will receive buprenorphine (Suboxone®; up to 24 mg daily) and will be randomly assigned to one of two groups. The experimental group (n=20) will receive daily remote observed dosing (ROD) via a secured video platform that records dosing using study-provided smartphones (approximately 5 minutes each session). ROD videos will be monitored daily for compliance. The attention control group (AC, n=20) dosing will not be observed. All subjects will attend 2 weekly study visits (3 study visits during the induction phase in Week 2). Study visits starting in Week 3, after the Induction phase, will consist of counseling in the form of weekly Medication Management (MM); buprenorphine distribution with medication management; and a urine screen. Study visit 4 will consist of a urine screen and phone management task (downloading study related videos) for those randomized to the Remote Observed Dosing Group.

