### **Laboratory Measurements (in alphabetical order)**

Blood chemistry, Complete Blood Count (CBC), and Urinalysis are obtained to assess for adverse events. Enzyme levels will be obtained once at baseline and end of the study.

Pregnancy Testing. Urine pregnancy tests will be obtained from all women at baseline, week 5, week 9, and end of study.

Urine Drug Screen and Urine Buprenorphine and Norbuprenorphine Screen. Quantitative urine buprenorphine and norbuprenorphine levels (using gas chromatography) with urine creatinine used as a control for urinary concentration will be assessed twice weekly throughout the trial. Urinary buprenorphine levels have been used extensively to establish buprenorphine adherence (Fox, Tetlow, and Allen 2006; Vincent et al. 1999). Quantitative levels of methadone have been used successfully to establish methadone compliance in a methadone maintenance program (Preston et al. 2003). Our toxicology consultant will assist us in interpreting urine creatinine controlled quantitative buprenorphine levels to establish medication adherence. Data from this trial will be used in optimizing the use of quantitative urine buprenorphine and norbuprenorphine levels in the subsequent efficacy trial. Qualitative (emit) urine toxicology for other drugs (benzodiazepines, barbiturates, opiates, marijuana, methadone, and amphetamine) is done at baseline and weekly throughout the trial.

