#### **4.3 Exclusion Criteria**

Exclusion Criteria (prior to induction):

- Current diagnosis of AIDS
- Participation in buprenorphine maintenance treatment within the past 3 months
- Presence of AST and/or ALT equal to or > 3X upper limit of normal
- Total bilirubin and/or creatinine equal to or > 1.5X upper limit of normal
- Current diagnosis of chronic pain requiring opioids
- Pregnant or lactating women
- Previous hypersensitivity or allergy to buprenorphine
- Current use of agents metabolized through CYP 3A4 such as azole antifungals (e.g. ketoconazole), macrolide antibiotics (e.g. erythromycin), and protease inhibitors (e.g. ritonavir, indinavir, saquinavir)
- Meet DSM - 5 criteria for current use disorder for any psychoactive substances other than opioids, marijuana, cocaine or nicotine (e.g. alcohol, sedatives)
- Current use of benzodiazepines
- Significant medical or psychiatric symptoms or dementia which in the opinion of the investigators would preclude compliance with the protocol, adequate cooperation in the study, or obtaining informed consent
- Concurrent medical conditions (such as severe respiratory insufficiency) that may prevent the patient from safely participating in the study; and/or any pending legal action that could prohibit participation and/or compliance in study procedures

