### **5   Study Procedures**

See Measures for Description of Study Assessments

See Table 1 for Assessment Schedule

**Regular evaluation visits.** Subjects will have appointments with study staff two times weekly throughout the 12-week medication phase of the trial. A telephone reminder call and/or text message will be used to enhance attendance. Urine drug screens (UDS) for buprenorphine and norbuprenorphine will be obtained at each visit, along with concomitant medications, adverse events, and time line follow back (TLFB). The Columbia Suicide Severity Rating Scale (CSSRS) will be obtained at baseline and weekly. Other measures completed routinely but not weekly are listed in Table 1. A description and schedule of assessments is provided in the study measures section of the protocol. Each patient will meet weekly with the clinician who will assess clinical status, dispense study medications and monitor adverse events and concomitant medications.

After the completion of Week 13, or at the termination for patients who discontinue from the trial prematurely, we will conduct the following procedures: physical exam, electrocardiogram, monitor adverse events and concomitant medications, obtain blood samples for chemistry, CBC, obtain a urinalysis (and a pregnancy test for women), and complete other measures (See Table 1). The Systems Usability Scale will be conducted at the end of study visit. Safety follow up visit will be conducted one month after the completion of the medication phase.

**Psychosocial Treatment.** Subjects will participate in weekly Medication Management (MM), an intervention developed as part of NIAAA's Project COMBINE study, that provides advice and support from medical practitioners concomitantly with dispensing medications, safety checking and compliance (Pettinati et al., 2004). The main goal of MM is to increase the likelihood that patients will reduce their opioid use. The initial MM session is an hour; subsequent sessions are 15-30 minutes.

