### **5.2.2 Visits 2-4 (Suboxone Induction)**

Participants who are appropriate for the trial will be inducted onto Suboxone® using standard office based induction as described in the ASAM National Practice Guideline for the Use of Medications in the Treatment of Addiction Involving Opioid Use (Kampman, Kyle and Jarvis, Margaret 2015).

- Concomitant medications
- Medical Management, Pill Distribution
- Adverse Events
- Visit 4: Randomization & Distribution of Smartphone w/ intervention training

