### **6.3.2 Analysis of Primary Outcome of Interest**

The primary comparison between the groups will use the creatinine normalized weekly quantitative urine levels for buprenorphine and norbuprenorphine. For each response, we anticipate that a response transformation, such as the log transform, will yield responses appropriate for group comparisons based on linear mixed effects models, but we will consider generalized linear mixed effects models if necessary. Comparisons of BIC statistics across different covariance structures will be used to select the best model for within subject correlations – typically a model with random intercept and ar(1) residual correlations provides a good fit. The main explanatory variable will be a binary indicator for group (ROD vs AC). Time will be regarded as a continuous scale, and linear, quadratic or spline trends will be used as necessary, with group by time interactions examined for significance. Our primary analyses will examine the two sets of responses (buprenorphine and norbuprenorphine) separately, but we will also consider bivariate mixed effects models with cross-correlation structure to assess strength of dependence and concordance between the two sets of measures. These analyses will be performed using PROC GENMOD in SAS.

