## 13 Appendices

**Table 1: Assessment Schedule**

| Assessment  | Baseline
(V1) | Week
2 (V2-
V4) | Weeks 3-14
(V5-V28) | End of
Study
(V29) |
|---|------------------|-----------------------|------------------------|--------------------------|
| Medical Exam and EKG, CBC and blood chemistry, Urinalysis (UA), Risk Assessment Battery           | 1X               |                       |                        | 1X                       |
| Pregnancy Test (women), Addiction Severity Index (ASI)  | 1X               |                       | 2X, weeks 5 and 9      | 1X                       |
| Urine Toxicology and Urine Buprenorphine and Norbuprenorphine Screen, Timeline Follow back (TLFB) | 1X               |                       | 24X                    | 1X                       |
| Clinical Global Impression Scale (CGI), Hamilton Depression Rating Scale (HAM-D)                  | 1X               |                       | 1X, week 9             | 1X                       |
| Columbia Suicide Severity Rating Scale (C-SSRS), Obsessive Compulsive Drug Use Scale (OCDUS)      | 1X               |                       | 12X                    |                          |
| Systems Usability Scale (SUS)   |                  |                       |                        | 1X                       |
| Concomitant Medications   | 1X               | 3X                    | 24X                    | 1X                       |
| Medical Management, Pill Distribution   |                  | 3X                    | 12X                    |                          |
| Adverse Events  |                  | 3X                    | 24X                    | 1X                       |
| Video Compliance/Attention Control (7 days per week, weeks 3-14)                                  |                  |                       | 84X                    |                          |

CONFIDENTIAL

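### Section 3 puts a urine screen at Visit 4 but Table 1 and Section 5.2.2 list none, so as scheduled the urine comparison has no on-treatment level from before the randomised intervention

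*Combined protocol and SAP*

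**What the plan says.** Four places in the combined protocol and SAP bear on urine around randomisation.

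- **Section 3:** "Study visit 4 will consist of a urine screen and phone management task". The sentence ends "for those randomized to the Remote Observed Dosing Group". It does not say whether the screen is the quantitative assay or whether it is taken before allocation.
- **Section 5.2.2:** the list for Visits 2-4 covers concomitant medications, medical management with pill distribution, and adverse events, and adds "Visit 4: Randomization & Distribution of Smartphone w/ intervention training". No urine is listed.
- **Table 1 (Section 13):** the urine and TLFB row has 1 at baseline, a blank for week 2 (Visits 2-4), 24 in weeks 3-14 and 1 at end of study. Video compliance or attention control runs in weeks 3-14.
- **General wording:** Section 3.3 (Laboratory Measurements) says that quantitative levels "will be assessed twice weekly throughout the trial". Section 5 says "Urine drug screens (UDS) for buprenorphine and norbuprenorphine will be obtained at each visit", in a paragraph about the 12-week medication phase. Neither settles Visit 4.

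Visit 1 comes before induction. Section 4.3 excludes "Participation in buprenorphine maintenance treatment within the past 3 months". For the primary between-group comparison, Section 6.3.2 says "The main explanatory variable will be a binary indicator for group (ROD vs AC"; it adds time trends and group-by-time interactions, and names no baseline urine level.

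**The concern.** Visit 4 is the only scheduled visit at which a urine sample could be both on treatment and before the randomised intervention. Visit 1 is too early, because participants have not yet been inducted. Visit 5 onwards falls in the monitored period. If Table 1 governs what staff do, no such sample exists, and it cannot be recovered later.

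This matters because urine levels differ between people for reasons other than adherence. Doses are individual (Sections 4 and 5.2.3), creatinine corrects only for urinary concentration, and the allocation factors in Section 3.2 include neither dose nor level. With 20 per arm, chance imbalance in level is plausible. The plan has no pre-intervention value with which to describe it, and none to use as a covariate to gain precision.

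**Working it through.** **Sample count.** Table 1 gives 1 + 0 + 24 + 1 = 26 urines per participant. Adding the Section 3 screen gives 27. On-treatment samples before the randomised intervention: 0 under Table 1, at most 1 under Section 3.

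**The plan's own figure.** Section 6.1 states 80% power for a linear group-by-time effect of d = 0.65, with alpha 0.05, within-subject correlation 0.4 and 10% dropout. Assumptions: two-sided test, constant correlation, a difference growing from 0 to 0.65 SD at the last of m occasions, and 20 x 0.9 = 18 per arm. The standardised contrast is 0.65 x sqrt(S/0.6)/(m - 1), where S is the sum of squared centred times. Power is the normal probability below sqrt(18/2) x contrast - 1.960.

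- m = 12: S = 143, contrast 0.912, 3 x 0.912 - 1.960 = 0.777, power 78.1%.
- m = 13: S = 182, contrast 0.943, 3 x 0.943 - 1.960 = 0.870, power 80.8%.

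The stated 80% is reproduced at 12 or 13 occasions. The number of occasions is not stated; 24 would give 96.0%.

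**Gain for the average group difference.** Inputs: T = 12 weekly values (Section 6.3.2 refers to weekly levels), total variance 1, Visit 4 one step before the first value. Let v be the variance of a participant's mean and c its covariance with the Visit 4 level. Adjustment leaves v - c²/1, so the proportional cut is c²/v. The detectable d at 80% power is (1.960 + 0.842) x sqrt(2 x variance/18).

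Constant correlation 0.4 (value from Section 6.1):

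- v = 0.4 + 0.6/12 = 0.450 and c = 0.4.
- Adjusted variance = 0.450 - 0.160 = 0.290; cut = 0.160/0.450 = 36%.
- Detectable d goes from 2.802 x sqrt(0.900/18) = 0.63 to 2.802 x sqrt(0.580/18) = 0.50.
- If only the Visit 4 correlation with later values drops to 0.2, the cut is 0.040/0.450 = 9%.

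Random intercept plus AR(1), the form that Section 6.3.2 describes as typical. The correlation at lag k is s + (1 - s)φ^k. The shares s and φ = 0.5 are assumptions; the documents give none. For s = 0.1, c = 0.1 + 0.9 x (sum of 0.5^k for k = 1 to 12)/12 = 0.175; the other rows follow in the same way.

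| Structure | v | c | Cut | Detectable d |
|---|---|---|---|---|
| s = 0.1, φ = 0.5 | 0.300 | 0.175 | 10% | 0.51 to 0.48 |
| s = 0.2, φ = 0.5 | 0.378 | 0.267 | 19% | 0.57 to 0.52 |
| s = 0.3, φ = 0.5 | 0.456 | 0.358 | 28% | 0.63 to 0.53 |
| Pure AR(1), φ = 0.4 | 0.179 | 0.056 | 2% | almost unchanged |

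**Gain for the slope.** Replace the mean by the least-squares slope weights. Under constant correlation the Visit 4 level has zero covariance with the slope, so the cut is 0%. In the four table rows the cut is 6%, 6%, 5% and 4%.

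**The case against.** The strongest reply is that the documents never promise a baseline. Section 3 says only that there is a urine screen. It may not be quantitative, it may follow allocation on the same day, and the closing words can be read as limiting it to the remote observed dosing group. On any of those readings there is no common baseline to lose. This stands, and it means the conflict has to be resolved by a decision; it cannot be assumed that a usable sample already exists. The one-arm reading makes reconciliation more necessary.

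A reader might infer that a planned analysis is broken or biased. The documents do not support that. Section 6.3.2 names no baseline level, and randomisation keeps the group comparison valid without one. What is missing is precision and a check on balance.

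A reader might also take 36% as the expected gain, or conclude that the power statement is wrong. The 36% needs a constant correlation of 0.4 between Visit 4 and every later sample, and it applies to the average difference. Section 6.1 powers a group-by-time effect, which gains little, and its 80% reproduces.

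Two further limits stand. Levels may not be stable at the end of induction, during which pills are distributed and not every dose need be observed. Doses can also be adjusted afterwards (Section 5.2.3), so a Visit 4 level does not reflect later dose. Nor is Visit 1 certain to be free of buprenorphine: Section 4.3 excludes recent maintenance treatment, not non-prescribed use. It is still a pre-induction sample and cannot serve as an on-treatment baseline.

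**Conclusion.** The conflict between Section 3 on one side and Section 5.2.2 and Table 1 on the other is real, and the general wording elsewhere does not resolve it. As scheduled in Table 1, there is no on-treatment level before the randomised intervention and no baseline level in the model.

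The benefit of repairing this is uncertain in size. For the average group difference it ranges from about 2% to 36% of the variance, with 10-28% under the assumed random-intercept plus AR(1) structures. These figures assume 12 weekly values, 18 per arm, equal variance at Visit 4 and later, and correlation parameters that the documents do not supply apart from the 0.4. The group-by-time contrast would gain 0-6%. The point is minor: an inexpensive improvement and a schedule correction.

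**What to change.** Reconcile Section 3, Section 5.2.2 and Table 1 so that each lists a urine sample at Visit 4, collected in both arms before allocation is revealed. State that it is run with the same creatinine-normalised quantitative buprenorphine and norbuprenorphine assay as later samples. In Section 6.3.2, pre-specify the log Visit 4 level of the corresponding analyte as a baseline covariate (or the same transform as the response, if another is chosen), and say how a missing Visit 4 value is handled.

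The cost is about 40 extra quantitative assays (one per participant) at a visit that already takes place, one degree of freedom in each model, and wording changes in three sections and one table. The SAP should acknowledge that the Visit 4 level may not be at steady state and does not capture later dose changes, so that it is used for precision and description of balance only.
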